7.9 Compliance

Data on total number and dose of ULT prescriptions issued in the preceding 12 months will be collected at each research visit, i.e. at years 1 and 2, and any unused ULT tablets counted. These will be used to calculate the medication possession ratio (MPR). The eightitem MMAS-8 will be completed at year 1 and year 2 research assessment visits.

7.10 Data collection in long-term extension phase:

Participants will continue to provide data about the occurrence of flares after their two-year research assessment visit for an additional two-year period. This will be in the form of a text message or paper diary depending on participant preference.

The GP surgery staff will search their records for GP consultations or hospitalizations due to gout, ULT prescription, other prescriptions for treating flares of gout, investigations, new diagnosis of cardiovascular diseases, hypertension, diabetes, incidence or progression of CKD, or death two years after each participant's last visit.

7.11 Criteria for terminating the trial

The trial will be stopped if:

[1] on an interim analysis there are overwhelming and undoubtable evidence of efficacy and/or major safety concerns,

[2] relevant new information become available, or

- [3] there are or issues with trial conduct such as
 - (a) poor recruitment,
 - (b) loss of resources.

The trial may be discontinued in one region if there is:

[1] poor recruitment, or

[2] poor adherence to the protocol.

The decision to terminate the trial in a single region or in all regions will be made after review by the TSC/DMC.

If this were to occur, all unused trial supplies e.g. medicines will be returned to the local NHS Pharmacies by the study participants for disposal as per usual NHS practice.

7.12 Laboratory analyses

Routine haematological and biochemical assessments such as full blood count, urea electrolytes and creatinine, liver function tests, and serum urate measurement will be performed in the local NHS hospitals in each region. The clinical pathology laboratories will

Page 47 of 71 Treat to target in gout Protocol Final Version 1.1 date 29 May 2019

use standard NHS practices to analyse and dispose of the samples in accordance with the Human Tissue Act, 2004.

7.13 Transport and storage of the tissues

Blood and urine samples for NHS pathology analysis will be labelled in accordance with local NHS procedures. Samples will be shipped and stored according to local protocols and no samples will be stored for research purposes following analysis.

8. STATISTICS

8.1 Statistical analysis plan

A detailed statistical analysis plan (SAP) will be drafted by the study statistician and approved by the TMG, the TSC and the DMC; it will be finalized before unblinding of the data (any subsequent deviations from the SAP will be approved by the TSC and documented in the final report). A summary of the statistical methods to be used is given below. The SAP will be the formal and up-to-date statement of all analyses to be performed on the trial data, and will take precedence over the study protocol in the event of any discrepancy in the analyses described by the two documents.

8.2 Internal Pilot

Analytical plan: Baseline categorical outcomes will be summarized using frequencies and percentages, and continuous outcomes will be summarized using means (standard deviations) and medians (interquartile range). Particular attention will be paid to missing items and patterns of missing data from the electronic capture of gout flare severity and QoL. No formal statistical comparisons between treatment arms will be made, but 95% CIs will be calculated for [1] the between-group difference in the gout flares count, between months 7– 12 in the two arms, and [2] the proportion meeting serum urate treatment target, and the between-group difference in these proportions, at month 12. Adherence with ULT will be assessed in the experimental and control arms (for control-arm participants who are on ULT using the MPR, taking the returned pill count into account, with a MPR \geq 80% or MMAS-8 >6 defined as being adherent [53]).

Signal of efficacy outcome measure and time-point: It is difficult to determine signal of efficacy from pilot studies. This is especially true for gout, where flares become more frequent in the first few months of initiating ULT, and continue for 6 months to 1 year (or even longer) after starting treatment. This is a direct effect of urate-lowering, which causes crystal dissolution, encouraging shedding of crystals in to the joint space which triggers a flare. In fact, gout treatment guidelines recommend flare prophylaxis (e.g. colchicine) for at least 6 months after starting ULT. In keeping with these, all study participants will be prescribed flare prophylaxis for 6 months in this study. Thus, we cannot use the number of flares in the first 6 months of ULT to gain a preliminary signal of efficacy. We will therefore estimate the number of gout flares in months 7–12 between the two arms. However, this does not form part of the thresholds to progress to the main trial (see below).

Threshold for progressing to the main trial: Page 48 of 71

Treat to target in gout Protocol Final Version 1.1 date 29 May 2019

The trial will proceed if the randomization rate from the main method of recruitment is $\geq 10\%$, $\geq 85\%$ data points in the flare diaries are completed by the participant, adherence with ULT is $\geq 80\%$ and attrition <20%, or pending revisions to the protocol if the randomization rate from the main method of recruitment is $\geq 5\%$, 70-84% data points in the flare diaries are completed by the participant, adherence with ULT is 60–79%, and attrition is 20–30%. If these thresholds are not met, discussion with the TSC and the HTA will take place to determine if modifications should be made to the procedures in the trial, or the trial should be terminated.

A main trial will be considered feasible if \geq 70% participants achieve serum urate target at month 12 in the intervention arm, and following protocol amendments if this proportion is >50%, with other *a priori* feasibility outcomes being met. Serum urate is a surrogate marker of frequent gout flares [9], and a reduction is a preliminary signal of efficacy. Additionally, a substantial reduction in serum urate in the intervention arm provides confidence that the intervention is being delivered as intended. However, we realize that this does not provide a direct measure of the primary outcome.

We do not propose to include gout flares in months 7–12 as an efficacy threshold of progression to the main trial due to the fact that gout flares may occur at the same rate even 1 year after starting ULT, and it would be erroneous to include it as a feasibility outcome. However, these data will be presented to the HTA Board and the Trial Steering Committee.

Rationale behind threshold for progressing to main trial

[1] A randomization rate of \geq 10% from the main recruitment method suggests that the recruitment will be completed from up to 50 GP surgeries as planned. If the recruitment rate is between 5% and 10%, we will approach additional GP surgeries via the NIHR Primary Care Clinical Research Networks. Given our experience of recruiting into gout studies from the primary care in the Midlands and Wessex (e.g. CONTACT study, PI [name]; and Nottingham study, PI [name]), we are confident of finding >100 willing GP practices for recruitment, and, the planned recruitment can be achieved if the randomization rate from main method of recruitment is as low as 5%.

[2] If target serum urate is not achieved in <50 participants by year 1, and <60% are adherent to ULT at year 1, it suggests such low concordance with the intervention that a meaningful effect on the rate of flare occurrence is unlikely, and proceeding with this trial would be futile.

[3] The sample size allows for up to 20% loss to follow-up. A high attrition rate of 21–30% in the pilot study likely indicates poor tolerability of the study processes, and we will explore and address the reasons for this. An attrition rate >30% will affect the validity of the findings, making proceeding with the study futile.

[4] If information in the electronic flare diary is 70–84% complete on any outcome measure (e.g. pain severity, flare stop date) we will address any problems. If the flare diary is completed in <70% instances for the primary outcome, this will not be a feasible method for collecting outcome data and other methods of collecting flare data, e.g. paper diary or phone calls, will be used.

Choice of method of outcome measure collection based on internal pilot: If the data quality (missingness) is substantially better in the paper diary, we will abandon the SMS system for collecting primary outcome data. Similarly, we will abandon the SMS for

Page 49 of 71 Treat to target in gout Protocol Final Version 1.1 date 29 May 2019

collecting primary outcome data if a substantial number of people phone in during/after their gout flare to provide data on primary outcome, and do not use real-time SMS.

Completeness of the flare diary in internal pilot

Participants can phone the CTU if they forget to send in text messages when they are experiencing a flare (see above). Apart from this, they will be sent text message reminders at 2 monthly intervals and requested to phone and inform the research team if there were any gout flares they did not report at all. This will be used to assess the completeness of the text message system in collecting data on the primary outcome (number of acute gout flares). Where a flare diary is initiated, we will measure the proportion of completed responses for each outcome of interest, i.e. erythema, pain severity, swelling and tenderness on day 1, EQ-5D-5L on day 2, daily pain score.

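### Read literally, the pilot's revisions rule admits only pilots with diary, adherence and attrition all in the middle band, so 13 of 16 acceptable result patterns meet neither progression rule

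*Protocol*

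**What the plan says.** Section 8.2 (Internal Pilot), under the threshold for progressing to the main trial, gives two joint rules and a fallback.

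- **Proceed rule.** It begins "The trial will proceed if the randomization rate from the main method of recruitment is" at least 10%, and adds diary completion of at least 85%, ULT adherence of at least 80% and attrition below 20%.
- **Revisions rule.** The trial goes ahead "pending revisions to the protocol if the randomization rate from the main method of recruitment is" at least 5%, "70-84% data points in the flare diaries are completed by the participant", "adherence with ULT is 60–79%, and attrition is 20–30" (per cent).
- **Fallback.** "If these thresholds are not met, discussion with the TSC and the HTA will take place to determine if modifications should be made" to trial procedures "or the trial should be terminated".

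The rationale that follows in section 8.2 takes criteria singly. Item [1] answers recruitment of 5-10% by approaching more surgeries. Item [3] says of attrition of 21-30%, "and we will explore and address the reasons for this". Item [4] answers diary completeness of 70-84% by dealing with the problems, and completeness below 70% for the primary outcome by changing the collection method. Item [2] addresses only adherence below 60%, together with poor urate control, and gives no middle-band action.

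A separate paragraph sets the serum urate criterion: feasible at 70% or more, and after amendments above 50%, provided the other feasibility outcomes are met.

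**The concern.** A three-level progression scheme should be ordered: improving one result should never move a pilot into a less favourable class. As worded, the revisions rule lacks this property, because three of its four conditions have a ceiling as well as a floor. A pilot that misses the proceed rule on one criterion and does well on the rest satisfies neither rule.

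This is the pre-specified basis for continuing a funded trial. Such criteria are fixed in advance so that the decision does not turn on interpretation once the pilot data are known. Here the rule and its rationale give different answers for most mixed results, so someone would have to choose between them after seeing the data.

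**Working it through.** **Inputs** (Protocol 8.2)

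| Criterion | Top band | Middle band in the revisions rule |
|---|---|---|
| Randomization rate | ≥10% | ≥5%, no ceiling |
| Diary completion | ≥85% | 70-84% |
| ULT adherence | ≥80% | 60-79% |
| Attrition | <20% | 20-30% |

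**The plan's own pilot figure.** Section 8.6 gives a 95% margin of error of about ±0.06 to ±0.08 for proportions of .1 to .2 with 90 participants. By 1.96·√(p(1−p)/90), the margin is 0.062 at p = .1 and 0.083 at p = .2. This reproduces. The progression thresholds are stated, not derived, so there is nothing else to recompute.

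**Enumeration.** Let each criterion be top (T) or middle (M), in the order randomization, diary, adherence, attrition. There are 2⁴ = 16 patterns with nothing below the middle band.

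- Proceed rule: TTTT only, 1 pattern.
- Revisions rule: the last three must all be M, and randomization may be T or M. TMMM and MMMM, 2 patterns.
- Neither rule: 16 − 1 − 2 = 13 patterns.

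By number of middle-band results:

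| Middle-band results | Patterns | Proceed | Revisions | Neither |
|---|---|---|---|---|
| 0 | 1 | 1 | 0 | 0 |
| 1 | 4 | 0 | 0 | 4 |
| 2 | 6 | 0 | 0 | 6 |
| 3 | 4 | 0 | 1 | 3 |
| 4 | 1 | 0 | 1 | 0 |

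No pilot with just one or two middling results reaches either rule. Each of the 13 has at least one T and no result below M, so it is at least as good as MMMM on every criterion and better on at least one.

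**Example.** Randomization 6%, diary 72%, adherence 62%, attrition 29% goes ahead with revisions. Randomization 12%, diary 90%, adherence 75%, attrition 10% misses the proceed rule on adherence, and misses the revisions rule because diary and attrition are too good.

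**Rule against rationale.** With the other three criteria in the top band:

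| Single middle-band result | Rationale | Literal rule |
|---|---|---|
| Randomization 5-10% | [1] approach more surgeries | neither rule |
| Attrition 21-30% | [3] explore and address | neither rule |
| Diary 70-84% | [4] address problems | neither rule |

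**Can this arise in practice?** The documents give no expected pilot results, so this is an illustration under assumed true attrition. An observed rate of 20% or more means at least 18 of 90. For X ~ Binomial(90, p), P(X ≥ 18) is 0.02 at p = .12, 0.12 at p = .15 and 0.35 at p = .18. One such result, with the other three criteria in the top band, meets neither rule.

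**Loose ends.** Attrition is 20-30% in the rule and 21-30% in rationale [3]. Diary values between 84% and 85%, and adherence between 79% and 80%, fall in no band. The urate criterion is outside the count, but it depends on the other outcomes being met and so inherits the ambiguity.

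**The case against.** The best answer is that the literal reading is not the natural one. The text sits under a heading about thresholds, and a pilot with 90% diary completion has, in ordinary language, met a 70% threshold. The first condition of the revisions rule is a plain floor, which suggests that the ranges only mark how far a result may fall short and still be acceptable. The rationale then explains a compressed sentence. Much of this stands: the intended 'at least' reading is fairly clear, and a sensible steering committee would probably apply it. It does not remove the fault, because the sentence that fixes the decision says something else.

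A reader might also infer that good pilots are sent towards termination. The documents do not support that. The fallback discussion names modification before termination, and section 7.11 requires TSC/DMC review before the trial is ended. For a pilot with one middling result, the discussion could end in much the same place as the revisions rule.

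Finally, 13 of 16 counts patterns; it is not a probability. The patterns are not equally likely, and the count shows no effect on power, bias or error rates. That is correct.

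**Conclusion.** The point holds as a defect of wording in a decision rule. On the literal reading, 13 of the 16 patterns with no criterion below its middle band meet neither progression rule, although each is at least as good throughout as the all-middle pilot that proceeds with revisions. This conflicts with the rationale's separate handling of recruitment, attrition and diary results.

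The count rests on taking 'and' as joint and the printed ranges as closed at both ends, and it leaves out the urate criterion. The effect is an incoherent progression rule that needs interpretation after the data are seen. It is minor: no pilot is stopped by it automatically, and the main-trial sample size and primary analysis are untouched.

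**What to change.** In section 8.2, replace the second rule with: *proceed after protocol revisions if every criterion is at or better than its lower limit (randomization ≥5%, diary ≥70%, adherence ≥60%, attrition ≤30%) and at least one is outside its proceed range.* The 16 patterns then split into 1 proceed, 15 proceed after revisions and 0 unclassified, and the gaps at 84-85% and 79-80% close.

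Keep the existing fallback sentence, with modification and termination both open, for any criterion beyond its lower limit. A rule that led only to a termination discussion would conflict with rationale [4], which answers diary completion below 70% by changing the collection method.

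At the same time, use one attrition band in the rule and in rationale [3] (20-30% against 21-30%), and check that the urate paragraph's reference to the other feasibility outcomes matches the reworded rule.

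The cost is one reworded sentence and one aligned figure. No lower limit or proceed threshold in the rule changes, and no extra data are needed.

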8.3 Full RCT

Analytical plan: Analysis will be on an intention-to-treat (ITT) basis, according to the prespecified SAP. The primary outcome, gout flare count over 24 month's post-randomization, will be analysed between groups through negative binomial regression, adjusting for flare count in the year prior to trial entry and stratification factor. If appropriate, a conditional, rather than a marginal, negative binomial model will be used to take account of flare count prior to trial entry (truncating these to be non-zero, in accordance with the corresponding inclusion criteria). The fit of a negative binomial model to the data will be assessed, and if poor, an alternative model (e.g. zero-inflated negative binomial or Poisson) will be used. As a secondary analysis on the primary outcome, flares occurring during months 1–12 and between months 13–24 will be analyzed between groups.

Longitudinal analyses based on generalized linear mixed-effects models will be performed for other continuous or binary outcomes, at both 1- and 2-year follow-up: mean pain intensity and mean duration of gout flares; mean serum urate; treatment satisfaction scores; adherence (those taking >80% of the doses or scoring ≥6 on the MMAS-8 will be considered as adherent) These analyses will similarly adjust for baseline values (where appropriate) and the stratification factor.

All analyses will take use all follow-up data where appropriate, using a generalized mixedeffects regression model, with a random intercept to account for the correlation between observations clustered within participants. Maximum likelihood estimation will be used to fit all the models, as this method of estimation yields parameter estimates that are not affected by the exclusion of missing outcome data if a missing-at-random assumption is plausible. Multiple imputation will be used for explanatory variables if missing at random is a plausible assumption.

Assumptions of all analyses will be checked and significance will be set at $p \le .05$, with 95% CIs calculated for between-group estimates. No adjustment will be made to alpha for multiplicity because the analysis of each outcome is of clinical interest in its own right. The primary analysis will be on the basis of ITT, but appropriate sensitivity analyses will be performed, as specified in the SAP.

Side-effects from intervention will be tabulated and compared between the two groups.

Page 50 of 71 Treat to target in gout Protocol Final Version 1.1 date 29 May 2019

Definition of CKD

Incident CKD will be defined as eGFR<60ml/min on 2 occasions at least 90 days apart. The results of eGFR at year 1 and year 2 research assessments will form one of the two qualifying results. If the eGFR at these research assessments is <60ml/min, the GP surgery records will be searched to identify a serum creatinine measurement in the preceding six months, and, if no such result is found or the previous eGFR is >60 ml/min, the GP will be advised to repeat the serum creatinine after 90 days as part of usual care of people with suspected incident CKD.

Progression of CKD will be defined as reduction in GFR of at least 25% and progression to next GFR category (KDIGO Definition). The results of serum creatinine, eGFR and urine albumin creatinine ratio at year 1 and 2 research assessments will be used to define the progression of CKD.

The proportion of people meeting the KDIGO classification of progression of CKD based on their eGFR and urine albumin creatinine ratio will be compared between the two groups at years 1 and 2 [51].

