6.1.2 Secondary outcome measures

- Number of gout flares in months 1-12
- Number of gout flares in months 13-24

Page 28 of 71

Treat to target in gout Protocol Final Version 1.1 date 29 May 2019

- Tophus count,
- Size of largest tophus,
- Daily pain score during gout flare,
- EQ-5D-5L during gout flares,
- GIS measured after flare resolution,
- Serum urate level: proportion hitting the target serum urate level (<360 µmol/L) at year 1 and 2,
- Serum urate level as a continuous variable at year 1 and 2,
- EQ-5D-5L between gout flares,
- ULT (name and dose),
- Treatment satisfaction,
- Returned pill count
- MMAS-8 scale,
- Serum creatinine and estimated GFR,
- Urine albumin creatinine ratio,
- Primary-care consultations for gout,
- Hospitalizations due to gout,
- Other prescriptions for treating flares of gout,
- Investigations for gout,
- Incident cardiovascular diseases, hypertension, diabetes,
- Incidence or progression of CKD,
- Death,
- Adverse events (AE), and
- Cost-effectiveness

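### The confirmation step for incident CKD does not follow its own 90-day definition, and the definition does not exclude participants who enter with eGFR 30–59

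*Protocol*

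**What the plan says.** The protocol lists "Incidence or progression of CKD" as a secondary outcome in section 6.1.2, and lists it again for the long-term extension in section 6.3.2. Section 8.3, under the definition of CKD, sets out both the definition and the steps for confirming it:

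- A new case requires "eGFR<60ml/min on 2 occasions at least 90 days apart".
- On where these values come from, the protocol adds: "The results of eGFR at year 1 and year 2 research assessments will form one of the two qualifying results".
- When a visit value is low, "the GP surgery records will be searched to identify a serum creatinine measurement in the preceding six months".
- A repeat is called for "if no such result is found or the previous eGFR is >60 ml/min". In that event "the GP will be advised to repeat the serum creatinine after 90 days".

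Progression of CKD is defined separately in the same section, by a fall in GFR of at least 25% together with a move to the next GFR category.

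On entry, section 6.7.2 excludes only stage 4/5 CKD, that is, eGFR below 30. The definition of incident CKD in section 8.3 states no minimum eGFR at screening.

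**The concern.** The definition has two parts: both values must be low, and they must be at least 90 days apart. The search step carries over only the first. It looks back six months with no minimum age for the result, and it switches off the repeat as soon as a result that is not above 60 is found. A low but recent result therefore blocks the repeat without being able to confirm the diagnosis.

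This is a rule about collecting data. If the repeat is not requested at the time, no later analysis plan can supply the missing result.

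The second difficulty is the at-risk set. People with eGFR 30–59 at entry are eligible, and the figure on flare prophylaxis in section 7.1 provides for eGFR 30–50. As worded, the definition would class long-standing reduced function in these people as incident disease.

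**Working it through.** No power or sample-size arithmetic applies. The check takes a participant with a visit eGFR below 60 and follows the rule in section 8.3 for each kind of earlier result.

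| Earlier result in the GP records | Definition met? | Repeat advised? | Outcome |
|---|---|---|---|
| None in six months | No | Yes | Resolved by repeat |
| Above 60, any age in the window | No | Yes | Resolved by repeat |
| Below 60, 90 days old or more (90, 120, 180 days) | Yes | Not needed | Confirmed |
| Below 60, under 90 days old (10, 45, 89 days) | No | No | Unresolved |
| Exactly 60, any age in the window | No | No | Unresolved |

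**Size of the band.** Six months is 365.25 / 2 = 182.6 days. Days 1–89 make up 89 / 182.6 = 0.49 of the window. This is a share of calendar time. It would be the share of earlier tests affected only if test dates were spread evenly over the six months, and the protocol gives no data on test timing. It is not a share of participants or of CKD cases. To fall in the gap a participant needs a low visit value, a low value under 90 days old, and no low value at least 90 days old. None of these frequencies is stated.

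**What the visits themselves recover.** Table 9 puts the year 1 and year 2 assessments at weeks 52 and 104, which are 52 weeks or 364 days apart. Two low visit values therefore satisfy the 90-day rule. Section 8.3 does not state this route, since it describes the visits as giving one of the two results, but the definition allows it. A participant left unresolved at year 1 who is still low at year 2 is recovered. A participant first low at year 2 has no later research visit within the two-year trial.

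**Entry with eGFR 30–59.** Take a participant at 50 at screening (week 0) and 50 at year 1 (week 52). Both values are below 60 and they are 364 days apart, so the definition is met although nothing has changed. The six-month search does not prevent this, because it does not reach back to screening. If no other test is on record, a repeat is advised, and a second low value again yields an incident case.

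**The case against.** **The wording can be read more kindly.** The text speaks of qualifying results, so the missing result could be understood as one that qualifies, meaning one at least 90 days old. That reading would close the first gap. However, the phrase directly follows "to identify a serum creatinine measurement in the preceding six months", which carries no minimum age, and whoever searches the records will act on what is written. The ambiguity is itself a reason to clarify.

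**Few cases are lost for good.** Low values at both visits recover some. Section 7.10 has GP records searched for CKD two years after the last visit, and section 8.5 analyses CKD as time to event, so some participants first low at year 2 may be picked up in the extension. GPs may also retest of their own accord. All of this stands and limits the size of the problem. It does not repair the two-year result, and the protocol does not ask for a retest in this branch.

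**The word incident implies a disease-free start, and the SAP can fix the risk set.** This is fair. Screening creatinine is collected, so the at-risk set can be identified, and under section 8.1 the SAP takes precedence on analyses. The definition as stated still does not exclude those entering at 30–59.

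**Readings that go too far.** A reader might infer a bias between arms from different testing frequency. The documents do not show one. Tables 9 and 11 schedule creatinine only at screening, year 1 and year 2, with no split by arm, and the titration visits specify serum urate only. The last scheduled treatment visit is week 29, which is 23 weeks (161 days) before year 1 and so outside the band. A reader might also infer that pairs of low values less than 90 days apart would be counted as CKD. Nothing in section 8.3 permits that, because the definition excludes them.

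**Conclusion.** The point holds as a minor inconsistency in how a secondary outcome is ascertained. On the literal text, a low earlier eGFR under 90 days old leaves the participant neither confirmed nor retested, and an earlier value of exactly 60 falls into the same hole. The band covers days 1–89 of about 183 in the search window. How many participants fall in it cannot be computed from the protocol, and the 49% should not be quoted as a proportion of cases. The unresolved cases are chiefly those first low at year 2.

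The definition also admits participants entering at eGFR 30–59 without any new disease. How many there will be is not stated either.

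The conclusion rests on reading the search sentence as written, and on there being no other low result at least 90 days old for the participant concerned. The primary flare outcome and the sample size are untouched. Table 12 lists CKD progression but not CKD incidence, which further limits the weight of the point.

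**What to change.** Reconcile the search and repeat steps in section 8.3 with the definition:

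1. Seek a confirmatory result whenever the records hold no eGFR below 60 dated at least 90 days before the visit. This also covers an earlier value of exactly 60.
2. State that low values at year 1 and year 2 together qualify.
3. Count incident CKD only among participants with screening eGFR of 60 or more. Use the screening value to define the at-risk set and not as a confirming value, since under this restriction it can never be below 60. Assess those below 60 at entry under progression.

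These changes concern how the outcome is ascertained and propose no change to treatment. The cost is a few sentences in section 8.3 and a few more confirmatory creatinine results. Screening creatinine is already collected, so no new baseline data are needed.
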